11.2 Sample size and recruitment

11.2.1 Sample size calculation

We considered different event rates, depending on the following assumptions. Firstly, we assumed that 30-50% of the participants may become infected with SARS-CoV-2 over the course of the study period. Of these, the percentage of participants who will experience the primary endpoint or laboratory test-confirmed symptomatic COVID-19 (i.e. any of the following: cough, shortness of breath or difficulty breathing, fever, chills, muscle pain, sore throat, new loss of taste or smell, nausea, vomiting, or diarrhea) is uncertain. We use a range of 15-50%. The estimated event rate is therefore $0.15 * 0.30 = 0.045$ (or 4.5%, rounded to 5%) to $0.50 * 0.50 = 0.25$.

We declare the superiority of a treatment arm if the probability that the Odds Ratio (OR) of the treatment is less or equal to 1 is greater than 95%, i.e. $P(OR < 1) > 95\%$. The remaining Bayesian statistical triggers of the adaptive trial are specified in section 11.5.

A 2-arm trial was simulated to assess the required sample size for the study. The OR was assumed to be 0.7. Three event rates for control arm were used: 5%, 10% and 15%. We are interested in the lower end of the 5-25% range for the control rate since a higher sample size is required when the event rate in the control arm decreases for a given effect size.

Figure 5 below reports the probability that the simulated trial concludes superiority of the treatment arm depending on the sample size per arm.

[figure not shown]

Figure 5: Sample size estimation for the first phase of the trial (2-arm)

The simulations show that the probability of declaring efficacy depends on the event rate in the placebo arm. With 2000-2500 participants per arm, even if the event rate is 5% in the control arm, the study has >80% chance to declare efficacy.

We propose to retain the option of reaching a maximum of 2,500 participants per arm. We will aim to enrol a maximum of 5,000 participants in total in the first phase of the trial to allow for possible loss-to-follow-up (LTFU), withdrawal, protocol deviation, non-adherence and other methodological challenges. Further phases may be added to the trial until a maximum of 30,000 participants is reached.

The assumptions underlying the sample size calculations will be reviewed at each interim analysis based on the observed data.

11.2.2 *Planned recruitment rate*

The participants for the first phase of the study are estimated to be recruited within 12 months, depending on the rate of site activation.

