11.4.2 Primary outcome analysis

The threshold for declaring that an education and surveillance plus therapeutic agent(s) arm is superior to education and surveillance plus placebo will be based on the OR for the specific arm compared to education and surveillance plus placebo. The objective is to obtain sufficient certainty (95% at least) that $OR < 1$. In mathematical terms, this quantity is referred to as $P(OR < 1) > 95\%$.

Primary analysis models:

The primary endpoint of incidence of symptomatic laboratory-confirmed COVID-19 infection will be analysed using a Bayesian logistic regression, including as covariates the treatment arm, age (<50 vs. ≥50), and a random effect for site.

The prior distribution corresponding to the education and surveillance plus placebo arm will be such that it is centered on 15% for the event rate, midway between the 5%-25% range that we consider. The prior distribution corresponding to the OR of the treatment arm will be such that the OR is centered on 1. Further details on the prior distributions are provided in the SAP.

Additional multivariable analyses will be conducted, taking into account the following variables: sex, smoking, body mass index, HIV infection, pre-existing respiratory disease, diabetes (recent HbA1c), hypertension, and coronary artery disease.

Secondary outcomes:

The endpoint of severity of symptoms on the WHO scale will be analysed using a Bayesian proportional odds model, using the same adjustment approach as the primary endpoint.

Other secondary outcomes that are binary in nature will be analysed using Bayesian logistic regression, using the same adjustment methods as previously described.

In addition, time-to-event models will be used to assess the effect of the interventions on the time to incidence of symptomatic laboratory-confirmed COVID-19 infection over the 150-day period since receiving trial interventions.

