11.5 Interim analyses

This Bayesian trial will perform frequent interim analyses for efficacy, futility and harm. This means that the DMC will regularly consider the balance of benefit and risk. Strong evidence of benefit, futility, or harm will result in the advice to modify or stop the trial.

The objective of interim analyses is two-fold: 1/ identify whether an active arm is futile, if the probability that its $OR \geq 0.9$ is high, greater than 95%, 2/ identify whether there is sufficient evidence that an active arm is superior to the control arm. The following table contains the statistical triggers for efficacy, futility and harm at interim analyses and for the final analysis.

Probability	Threshold at interim analysis	Threshold at final analysis	Evidence for:
$P_1 = P(OR < 0.8 \mid \text{data})$	99%	95%	Marked clinical benefit
$P_2 = P(OR \geq 0.9 \mid \text{data})$	99%	95%	Non clinically relevant (i.e. futile) treatment (or harm when $OR \geq 1$)

Posterior predictive probabilities will also be calculated at each interim analysis to inform the potential adaptation decisions.

Platform trial

In the study there exists a possibility of adding treatment arm(s) at interim analysis or during the course of the study. If a treatment arm is added, all comparisons will be made with concurrent control participants.

For the main effects of individual treatments (i.e. when given on their own), the thresholds for superiority and futility described above will apply to the same manner to the additional treatment(s).

For treatments that are given in combination in the context of a potential factorial design, the quantity of interest will be $P(\text{interaction term} < 1 \mid \text{data}) \geq 0.95\%$ (or 99% at interim analysis) to declare evidence of synergy. The prior distribution for the interaction term will be specified in exactly the same way as the prior of the OR of the individual treatments. Only its interpretation changes.

The SAP contains additional details regarding the monitoring of the trial, including the cumulative probability of declaring efficacy depending on the underlying simulated hazard ratio.

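### The single >80% figure for 2,000–2,500 per arm at a 5% control rate does not follow at 2,000 from the printed inputs; an informative control prior could supply it, but only with a raised false-positive rate

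*Combined protocol and SAP*

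**What the plan says.** Section 11.2.1 describes a simulated two-arm trial with an OR of 0.7 and control event rates of 5%, 10% and 15%. Superiority is declared when P(OR<1) exceeds 95%. For the lowest rate it concludes: "With 2000-2500 participants per arm, even if the event rate is 5% in the control arm, the study has >80% chance to declare efficacy". It continues: "We propose to retain the option of reaching a maximum of 2,500 participants per arm", and then: "We will aim to enrol a maximum of 5,000 participants in total in the first phase of the trial to allow for possible loss-to-follow-up", adding withdrawal, protocol deviation and non-adherence to the list. No loss rate is given.

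Section 11.3 gives 1:1 allocation. Section 11.4.2 repeats the 95% rule and describes the priors. The control-rate prior is "centered on 15% for the event rate, midway between the 5%-25% range that we consider". For the treatment effect: "The prior distribution corresponding to the OR of the treatment arm will be such that the OR is centered on 1". The widths are left elsewhere: "Further details on the prior distributions are provided in the SAP". Section 11.5 plans frequent interim analyses and says that the SAP holds further monitoring detail, "including the cumulative probability of declaring efficacy depending on the underlying simulated hazard ratio".

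**The concern.** One probability is attached to a range of sample sizes that differ by a quarter, although power changes appreciably over that range. The lower end matters because the 5,000 cap is presented as already covering losses. Since 5,000 = 2 × 2,500, nothing is added above the top of the range. The allowance is real only if clearly fewer than 2,500 evaluable participants per arm still give more than 80%.

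If the figure at 2,000 comes from the planned priors instead, a second matter arises. A control prior centred on 15% pulls the estimated control rate upward when the true rate is 5%. That makes treatment look better whether or not it works, so the gain in power brings extra false positives that a reader of section 11.2.1 would not see.

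**Working it through.** **Inputs.** Control rate 5%, OR 0.7, rule P(OR<1) > 95% (sections 11.2.1 and 11.4.2); two arms, 1:1 (sections 11.2.1 and 11.3). Prior centres are 15% for the control rate and 1 for the OR (section 11.4.2). Prior widths, number of looks and loss rates are not given, so all values used for them below are assumptions.

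**Step 1: treated rate.** Control odds 0.05/0.95 = 0.05263; × 0.7 = 0.03684; rate = 0.03684/1.03684 = 3.553%.

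**Step 2: vague priors, one analysis.** The rule is then close to a one-sided 5% test on the log OR. The variance is [1/(0.05 × 0.95) + 1/(0.03553 × 0.96447)]/n = (21.05 + 29.18)/n = 50.23/n, and power = Φ(0.3567/√(50.23/n) − 1.645).

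| Evaluable per arm | SE | Power |
|---|---|---|
| 2,000 | 0.1585 | Φ(0.606) = 72.8% |
| 2,250 | 0.1494 | Φ(0.742) = 77.1% |
| 2,500 | 0.1417 | Φ(0.871) = 80.8% |

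Exact enumeration of the flat-prior model gives 73.3%, 77.5% and 81.2%. The plan's figure is therefore reproduced at 2,500 but not at 2,000.

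**Step 3: sample size for 80%.** n = (1.645 + 0.842)² × 50.23/0.3567² ≈ 2,441. A pooled-variance formula gives 2,418. The margin below 2,500 is (2,500 − 2,442)/2,500 = 2.3% to (2,500 − 2,418)/2,500 = 3.3%.

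**Step 4: assumed losses from 2,500 per arm.** 5% leaves 2,375 (79%), 10% leaves 2,250 (77%) and 20% leaves 2,000 (73%). This counts missing outcomes only; non-adherence would also dilute the effect.

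**Step 5: planned prior centres, assumed widths.** The model is a two-parameter Bayesian logistic regression without age or site. The control log-odds prior is normal, centred on logit(0.15); the log-OR prior is normal, centred on 0, with SD from 0.5 to flat. Exact binomial enumeration was used. One way to read the 5%–25% range as a width is [logit(0.25) − logit(0.05)]/3.92 = (−1.099 + 2.944)/3.92 = 0.47.

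| Control logit SD | Power at 2,000 | at 2,250 | at 2,500 | Type I error, 5% control |
|---|---|---|---|---|
| 0.47 | 84–85% | 86–88% | 89–90% | 8–10% |
| 0.5 | 82–84% | 85–87% | 88–89% | 8–9% |
| 0.75 | 76–79% | 80–82% | 84–85% | 6–7% |
| 1 | 74–76% | 78–80% | 82–84% | 5–6% |
| 2.5 or wider | 70–74% | 75–78% | 79.5–82% | 4–5% |

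Reaching 80% at 2,000 needs a control SD of about 0.57 (log-OR SD 0.5) to 0.66 (flat) or less. At those limits type I error is about 7%, and tighter control priors raise it further.

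**Step 6: repeated looks, vague priors.** With 1 to 10 equally spaced looks, an interim trigger of P(OR<0.8) > 99% and a final rule of P(OR<1) > 95%, power stays at 73% (2,000) and 81% (2,500). Five looks all at P(OR<1) > 95% give about 80% at 2,000, with a false-positive rate near 13%.

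**Step 7: other control rates.** By the Step 2 formula, 2,000 per arm gives 93% at 10% control and 98% at 15%.

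**The case against.** The strongest objection is that the plan never calls its priors vague. Section 11.4.2 names a control prior centred on 15% in the same sentence as the 5%–25% range. If its width roughly matches that range, the stated figure holds across the whole interval. Going from 2,000–2,500 to a 2,500 maximum that allows for losses is then coherent, and covers up to 20% loss. This stands, and it is why the sentence cannot be called an arithmetic error. A reader might infer from the 73% that the sponsor's simulation is wrong. The documents do not support that: Figure 5 is not visible in the text available, and the prior widths and monitoring detail are assigned to the SAP. The objection leaves the false-positive cost unanswered, however, because the width that gives 84–85% also gives a type I error of about 8–10%.

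Repeated looks cannot be excluded in general. Step 6 pairs an interim trigger from section 11.5 with the final rule of section 11.2.1, and that pairing is an assumption. The section 11.5 table sets its own final threshold for marked benefit on OR<0.8.

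The sentence can also be read loosely, as saying that 80% is crossed somewhere between 2,000 and 2,500. With vague priors that is true, at about 2,420–2,440, but the loss margin is still only 2–3%.

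Finally, the consequence is limited. The operative number is the 2,500 maximum, 5% is the lowest rate simulated, and section 11.2.1 says that the assumptions will be reviewed at each interim analysis.

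**Conclusion.** The point holds in conditional form. With vague priors and one analysis, the range figure is about 7 points short at 2,000 per arm and 3 points short at 2,250, and the first-phase cap leaves about 2–3% for losses. With a control prior tight enough to give 80% at 2,000 (logit SD about 0.57–0.66 or less), the power is delivered, but type I error at a 5% control rate is about 7% or more.

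Two stronger readings should be avoided. The first is that the trial is underpowered at its maximum. The >80% figure stands at 2,500, except that wide control priors (logit SD 2.5 or more) with a sceptical OR prior (log-OR SD 0.5) give about 79.5–80%. The second is that the loss allowance is 2–3% whatever the priors; that holds only when they are near flat. The shortfall is specific to the 5% control rate. The calculations leave out age and site effects and rest on assumed prior widths, looks and loss rates.

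**What to change.** In section 11.2.1, replace the range sentence with separate values, for example: *At a 5% control rate and an OR of 0.7, the probability of declaring efficacy under the planned priors is [a]%, [b]% and [c]% with 2,000, 2,250 and 2,500 evaluable participants per arm; type I error at a 5% control rate is [d]%, [e]% and [f]%. With vague priors and a single analysis the probabilities are about 73%, 77% and 81%.* The sponsor fills the bracketed values from its own simulation.

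Replace the statement that 5,000 allows for losses with the probability at the expected evaluable number. With vague priors and an assumed 10% loss, that is about 77% at 2,250 per arm.

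The cost is wording and a re-run of the existing simulation under OR = 1, with no added enrolment. The downside is that the stated figure becomes less favourable at the lower end, or its false-positive cost becomes visible.

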11.3 Randomization methods

Participant-level randomization will be used in the study.

The randomization sequence will be computer generated with permuted blocks. There will be initially equal numbers of participants (1:1) in each of the groups. Randomization will be stratified by age (<50 and ≥50) and site.

If the education and surveillance plus placebo arm is discontinued at an interim analysis, participants from this arm will be randomized to the remaining arms.

Modifications to the number of active treatment arms

Other arms can be added to CROWN CORONATION if evidence emerges that there are other suitable candidate prophylaxis options.

Participants will only be randomized to arms for which they are eligible. (e.g. pregnant women will not be randomized to the “vaccine vs placebo” arm).

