7.1.2 Trial participant exclusion criteria

Exclusion criteria (these could be modified depending on the choice of interventions in the platform trial)

1. Weight outside range 50 kg – 120 kg (110 lbs – 265 lbs).
2. Prior enrolment into this or other COVID-19 interventional prevention or treatment trials (observational trials not excluded).
3. Self-reported or laboratory confirmed previous or current diagnosis of SARS-CoV-2 or COVID-19.
4. Self-reported current acute respiratory infection.
5. Concurrent and/or recent use of the investigational product/s, a product considered to be equivalent to the investigational product/s, or any other product that is likely to interfere with the investigational products in this trial or the interpretation of the trial data.
6. Self-reported known allergies to any of the IMPs and excipients of the IMPs and placebo.
7. Self-reported presence or history of the conditions listed in the appendix relevant to that IMP
8. Self-reported current use of medication with known to interact with any of the medications listed in the appendices.
9. Inability or unwillingness to be followed up for the trial period.

Additional to the set of exclusions in the core protocol, each arm of the trial (e.g. “MR vs Placebo” arm or “MMR vs Placebo” arm) will have their own set of additional exclusion criteria (refer to the appendix). Participants will only be randomized to those arms for which they are eligible.

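### From the factorial phase on, the plan does not limit an arm's placebo controls to participants who could have been allocated to that arm

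*Combined protocol and SAP*

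**What the plan says.** - **Allocation.** Section 7.1.2 gives each arm its own exclusions on top of the core ones and adds: "Participants will only be randomized to those arms for which they are eligible". Section 11.3 repeats the rule, "Participants will only be randomized to arms for which they are eligible", and gives an example: "pregnant women will not be randomized to the “vaccine vs placebo” arm".
- **Arms.** Section 3 (part D) starts with two arms, vaccine and placebo, for an estimated 5,000 participants. It then moves to a 2-by-2 design with Drug A and later to a 2-by-2-by-2 design. Each factorial design lists a single placebo-only arm (Arm 1).
- **Comparison.** Under Section 11.4.2 the superiority decision "will be based on the OR for the specific arm compared to education and surveillance plus placebo".
- **Controls.** Section 11.5: "If a treatment arm is added, all comparisons will be made with concurrent control participants".
- **Model and analysis set.** The primary logistic regression is specified as "including as covariates the treatment arm, age (<50 vs. ≥50), and a random effect for site". Section 11.6 makes an intention-to-treat analysis of all randomised participants the main strategy. The set of arms open to a participant is neither a covariate nor a stratification factor (Sections 5.1, 8.2 and 11.3).

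**The concern.** Someone ineligible for the vaccine can still enter the factorial phase. Pregnancy is the protocol's own example: it is not a core exclusion in Section 7.1.2, and Section 8.5 plans follow-up of women who are pregnant at entry. Such a participant would be randomised between Drug A and placebo. The only placebo-only arm listed is Arm 1, which is also the vaccine's control.

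The restriction to concurrent controls deals with drift over time. It does not ensure that both sides of a comparison come from the same eligible population. If ineligible placebo participants are counted as vaccine controls, the contrast mixes a randomised comparison with a non-randomised one. Arm-specific exclusions are conditions and interacting medications, which may plausibly be related to COVID-19 risk, exposure or symptom reporting. Age group and site need not capture that. The comparison at stake is the one that decides the primary endpoint, and the error can run in either direction.

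**Working it through.** **1. The plan's own figure.** Section 11.2.1 gives more than 80% chance of declaring efficacy with 2,000–2,500 per arm, at a 5% control rate and OR 0.7. The treated odds are 0.7 × 0.05/0.95 = 0.0368, a rate of 3.55%. I treat P(OR<1)>95% under a vague prior as a one-sided 0.05 test. Power is then 81.2% at 2,500 per arm and 73.1% at 2,000. The figure reproduces at the planned maximum but not at the lower end of the range. The present point does not depend on it.

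**2. Share of ineligible people in Arm 1 (2-by-2 phase).** Let q be the fraction of entrants who are ineligible for the vaccine but eligible for Drug A. With equal allocation, eligible people go 1/4 to each of four arms. Ineligible people go 1/2 to each of the two arms without vaccine.

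s = (q/2) / [(1−q)/4 + q/2] = 2q/(1+q)

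- q = 2%: s = 0.04/1.02 = 3.9%
- q = 5%: s = 0.10/1.05 = 9.5%
- q = 10%: s = 0.20/1.10 = 18.2%

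Pooling the factorial margins (vaccine against no vaccine) does not help: q / [(1−q)/2 + q] is again 2q/(1+q).

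**3. Apparent OR when the vaccine has no effect.** Let r be the risk ratio of ineligible to eligible people, with 5% risk in the eligible. Placebo risk is p = 0.05 × [(1−s) + s·r]. For q = 10%, r = 2: p = 0.05 × (0.818 + 0.364) = 5.91%. OR = (0.05/0.95)/(0.0591/0.9409) = 0.84.

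**4. Chance of meeting P(OR<1)>95%.** By normal approximation on the log OR with 2,500 per arm, for the same case:

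- SE = √[1/(2,500 × 0.05 × 0.95) + 1/(2,500 × 0.0591 × 0.9409)] = 0.125
- log OR = −0.177
- probability = Φ(0.177/0.125 − 1.645) = 41%

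| q | r | OR for a null vaccine | P(OR<1)>95% met |
|---|---|---|---|
| 2% | 0.5 | 1.02 | 4% |
| 2% | 1.25 | 0.99 | 6% |
| 2% | 2 | 0.96 | 9% |
| 5% | 1.25 | 0.98 | 7% |
| 5% | 2 | 0.91 | 19% |
| 10% | 0.5 | 1.11 | 1% |
| 10% | 1.25 | 0.95 | 10% |
| 10% | 1.5 | 0.91 | 18% |
| 10% | 2 | 0.84 | 41% |
| any | 1 | 1.00 | 5% |

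A simulation that adds the ineligible controls on top of 2,500 eligible ones gives 42.9% for the q = 10%, r = 2 case, so the result is not sensitive to that choice. More participants do not cure the bias: at 5,000 per side the 41% becomes 64%.

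**5. The other direction.** With q = 10% and r = 0.5, a true OR of 0.70 would appear as 0.70 × 1.105 = 0.77.

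**6. After the fix.** With controls limited to people eligible for the arm, the null OR is 1.00 and the simulated rate is 5.0%.

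The documents give neither q nor r; both are assumptions. The 2,500 per arm is the first-phase maximum, carried over to the factorial phase for illustration.

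**The case against.** A reader might infer that the plan commits to using every concurrent placebo participant, ineligible ones included. It does not say so. In "all comparisons will be made with concurrent control participants" the word *all* qualifies the comparisons, not the controls, and the sentence is aimed at non-concurrent data. The example in Section 11.3 names the vaccine-versus-placebo comparison as the unit of eligibility, and Section 7.1.2 uses the same unit. Read that way, an ineligible person is kept out of both sides. This stands as evidence of ambiguity. It does not settle the matter: the example governs allocation, no sentence carries it into the analysis set, and the factorial phase has no separate vaccine-versus-placebo arm to which it could apply.

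A reader might also infer that randomisation itself is broken. It is not: allocation remains random within each eligibility set, and the issue is who enters each analysis.

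Other points that stand, in whole or in part:

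- The first phase has one active agent, so a vaccine-ineligible person has no other comparison to enter. The problem cannot arise there.
- Section 11.4.2 plans further multivariable analyses (including sex, body mass index, HIV and diabetes) that may overlap with reasons for ineligibility. They might reveal the confounding, but they supplement the primary model and do not replace it.
- The Section 11.5 final trigger for marked benefit is P(OR<0.8) at 95%. In the worst case above a null vaccine meets it only about 2% of the time. Section 11.4.2, however, declares superiority on P(OR<1), and the estimate is biased under either trigger.
- Section 11.4 is an overview. The detailed SAP and the arm appendices are not in the reviewed text and may define the comparison sets.

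**Conclusion.** The point holds as a gap in how the comparison sets are defined, from the 4-arm phase on. Eligibility differs by arm, the placebo arm is shared, controls are limited only by time, all randomised participants are analysed, and the model ignores eligibility. Taken together and followed literally, these rules place vaccine-ineligible placebo participants among the vaccine's controls.

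The size is conditional. Over q = 2–10% and r = 0.5–2, a null vaccine shows an OR between about 1.11 and 0.84, and the superiority criterion is met about 1% to 41% of the time instead of 5%. The 41% needs both 10% ineligible and double risk, so it is the edge of an assumed range and should not be read as a forecast. At r = 1.25 the rate is 6–10%, and at equal risk there is no bias. Because the bias can go either way on the primary endpoint and the remedy costs almost nothing, this should be settled in the text and not left to interpretation.

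**What to change.** Before a second agent opens:

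- In Section 11.5 and the SAP, define the controls for each arm as participants randomised concurrently who were eligible for, and could have been allocated to, that arm.
- Apply the same rule to any pooled factorial main effect.
- Record in the randomisation system, at the time of randomisation, the set of arms open to each participant, and use that variable to build each comparison set. Reconstructing it later is error-prone.

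The cost is a short text change and one stored variable. Each comparison loses a few controls, all of them people who could not have been allocated to the arm under test. The initial 2-arm phase needs no change.
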